#### *Missing Data*

The study will implement multiple procedures to prevent and reduce the amount of missing data and use appropriate statistical procedures to evaluate whether the results are robust to missing data. The risk of missing patient-reported outcome measures has been reduced by limiting the number of visits and assessments to those essential to achieve study goals and using “short” versions of instruments to

reduce burden. It is possible, however, that there may be some nonresponse to the 6- and 12-month patient reported outcome surveys. The sample size calculation assumed as high as 25% non-response at 12 months. EHR-derived data on opioid dosage is expected to be virtually complete based on standard PCORnet data extraction procedures, yet sample size calculations allow for up to 12% missing data at 12 months from lost to follow-up within the EHR or withdrawal of consent for use of EHR data. To reduce the risk of being unable to calculate the primary outcome because of missing or uninterpretable dosing instructions, MED will be derived using only the standardized and highly accurate fields: drug name, strength, and number of pills. In the event of missing medication information for a prescription (such as strength or number of pills), we will impute medication information from the 2 closest prescriptions by date, using an algorithm developed by our clinical content experts, and conduct sensitivity analyses with and without the imputed data.

Logistic regression models will be used to compare the demographic characteristics of participants who provided 18 months of EHR data as compared with participants who were lost to follow-up within the EHR or withdrew consent for study participation to identify possible differential attrition. For primary and secondary outcomes analysis, the planned likelihood-based analysis will produce unbiased results if the data are MAR; that is, not related to the unobserved value of the outcome, but can be related to observed values of the outcome or model covariates.

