9.4 Sensitivity and Supportive Analyses of the Primary Outcome

Supportive Analyses

- The primary analysis will be repeated for the per-protocol population.
- As an *exploratory* analysis, the primary analysis may also be repeated for the modified intent to treat (MITT) population (defined below).
 - The MITT population in this study is defined as any randomized participants that received at least some of the study treatment (“randomized and treated”), defined as at least one SDM, MI, or CBT visit.
- Percentage change in daily MED from the baseline period also will be evaluated in a supportive analysis of the primary outcome. In this analysis, rather than change from baseline, each timepoints value will be calculated as the percent change, calculated as the change divided by the baseline score. The statistical model is the same.
- Compare the percentage of participants across intervention group that have met the clinically significant decrease in opioid use from baseline, defined as a decrease of 10 MED daily dose.
 - This analysis will be performed with a logistic mixed model for repeated measures (Proc GLIMMIX), similar to the method described in section 9.6.2 below.

Sensitivity Analyses - Assessment if Baseline Characteristics are Associated with Missing Outcome Data

This assessment will only be conducted if the percentage of participants with missing MED data at the 12-month timepoint is more than 20% in the ITT population.

A logistic regression model will be used to compare the demographic characteristics of participants who provided 12 months of EHR (prescription) data as compared with participants who were lost to follow-up within the EHR or withdrew consent for study participation to identify possible differential attrition. These characteristics will include but are not limited to: age, race, sex, baseline pain, baseline opioid use, co-

morbid health conditions, and others. In the event this logistic regression model indicates that a specific baseline characteristic is associated with a higher rate of attrition (or missing data), it can lead to biased results for both the primary and secondary outcomes.

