If results of the logistic regression model indicate a specific baseline characteristic is associated with missing data, a sensitivity analysis on both the primary and secondary outcome measures will be implemented that run a similar model to those proposed in Sections 9.3 and 9.5 respectively, but the model will also include the baseline characteristic (i.e.: covariate) found to be associated with missing data.

Sensitivity Analyses - Multiple Imputation

This sensitivity analysis will only be conducted if the primary analysis identifies a statistically significant treatment group difference at 12 months in the ITT population and if the percentage of participants with missing MED at the 12-month timepoint is more than 20% in the ITT population. The MMRM analysis approach assumes missing data due to early study discontinuations are missing at random (MAR). As a sensitivity analysis to guard against bias if the MAR assumption is incorrect, a sensitivity analysis will be conducted on the primary outcome to assess the robustness of the primary analysis results using methods that assume that data are missing not at random (MNAR). Specifically, we will use multiple imputation of missing data to generate multiple imputed complete datasets, analysis of covariance on each dataset, and Rubin's rule to compare treatment groups across the imputed datasets (Ratitch, 2014). We will explore one sensitivity analysis called a tipping point analysis: impute missing outcomes in the intervention found to have a weaker change from baseline at varying percentages of the observed data (i.e., decreasing the observed MED) until a statistically significant treatment group difference is no longer identified (O'Kelly and Ratitch, 2014). This analysis tells us how much difference in the data could be present in order to still identify a statistically significant difference.

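### The attrition model in SAP 9.4 names no study arm, so a baseline characteristic that predicts loss in opposite directions in the two arms can go unflagged

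*SAP*

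**What the plan says.** SAP 9.4 makes the attrition assessment conditional on "missing MED data at the 12-month timepoint is more than 20% in the ITT population". One logistic regression is then to "compare the demographic characteristics of participants who provided 12 months of EHR (prescription) data as compared with participants who were lost to follow-up" or who "withdrew consent for study participation to identify possible differential attrition". The predictors are described as follows: "These characteristics will include but are not limited to: age, race, sex, baseline pain, baseline opioid use", with comorbid conditions and unspecified others added. Study arm, an arm-by-characteristic term and separate fits by arm are not mentioned.

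The consequence is set out in the same section. "If results of the logistic regression model indicate a specific baseline characteristic is associated with missing data", the primary and secondary outcome models are rerun and "the model will also include the baseline characteristic (i.e.: covariate) found to be associated with missing data". No significance threshold is given for that decision.

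Protocol 5.3.3 (Missing Data) has a comparison of the same kind at 18 months, also without arm: "Logistic regression models will be used to compare the demographic characteristics of participants who provided 18 months of EHR data".

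The primary model in SAP 9.3 already contains arm, time, arm-by-time, baseline opioid dose and institution, and uses MED from months 3 to 18. The tipping-point analysis in SAP 9.4 runs only if the primary result is significant and more than 20% of 12-month MED is missing.

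**The concern.** The aim is "to identify possible differential attrition". In a randomised comparison, a characteristic that predicts loss equally in both arms, with equal loss overall, leaves the arm difference almost unbiased. The troublesome pattern is a prognostic characteristic whose relation to loss differs by arm. A model without arm estimates roughly the average of the two arm-specific slopes, so slopes of opposite sign cancel.

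Arm-specific loss is not far-fetched here. The trial is open-label. One arm may involve a change of opioid provider (Protocol 6.2.1). The other asks for an MI session and up to 8 group sessions, possibly with co-pays (Protocol 6.3.1 and 8.1.3). SAP 5.2 expects a different form of nonadherence in each arm.

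At stake is the covariate-adjusted sensitivity analysis. A characteristic that is not flagged is not added to the model, and after a non-significant primary result no tipping-point analysis follows either.

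**Working it through.** **The plan's own figures.** With a 10-MED difference, SD 40, two-sided 0.05 and 80% power, the normal formula gives 252 per arm, against 253 stated. 506 x 1.2 = 607.2, stated as 608. At 526 randomised, power is 74.4% (526/1.2 evaluable) to 76.7% (526 x 0.88 evaluable), against 75% stated. These reproduce and are not in dispute. The attrition model has no figure of its own beyond the 20% trigger.

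**Chance of flagging a characteristic.** Assumptions not in the documents: 263 per arm, 23% loss in each arm, a standardised characteristic X, and a flag at p < 0.05. Let b1 and b2 be the log-odds of loss per SD of X in the two arms.

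- SE of the pooled slope: s = 1/sqrt(526 x 0.23 x 0.77) = 1/sqrt(93.15) = 0.104
- Pooled test: z = |b1 + b2| / (2s)
- Interaction test, whose SE is 2s: z = |b1 - b2| / (2s)

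| b1, b2 | Pooled z, flagged | Interaction z, flagged | Simulated, pooled vs interaction |
|---|---|---|---|
| +0.4, -0.4 | 0, 5% | 3.86, 97% | 4-6% vs 95-98% |
| +0.4, -0.2 | 0.97, 16% | 2.90, 82% | 16% vs 80% |
| +0.4, 0 | 1.93, 49% | 1.93, 49% | 44% vs 48% |
| +0.7, 0 | 3.38, 92% | 3.38, 92% | 89-90% vs 88-91% |
| +0.4, +0.2 | 2.90, 82% | 0.97, 16% | 84% vs 14% |
| +0.4, +0.4 | 3.86, 97% | 0, 5% | 95% pooled |

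The formulas mark the boundary. The interaction test does better when the two slopes have opposite signs, the tests tie when one slope is zero, and the pooled test does better when the signs agree.

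A separate simulation used a binary characteristic at 50% prevalence, 25% loss and 2,000 runs. With odds ratios of 2 and 1/2, the flag rates were 4.8% (pooled) and 92% (interaction). With an odds ratio of 2 in one arm only they were 41% and 40%. Adding arm as a main effect alone does not help: with opposite slopes and equal loss, the arm term is significant in about 5% of trials.

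**Bias if only 12-month completers were compared.** The mean of X among those retained shifts by about -b x 0.23. With slopes +b and -b, and X worth g MED per SD:

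bias = 2 x b x 0.23 x g

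- b = 0.4, g = 10: 1.8 MED
- b = 0.4, g = 16: 2.9 MED
- b = 0.7, g = 16: 5.2 MED

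Simulation gave 1.7-3.0 MED for the first two and about 5 MED for the third. With X in the outcome model the bias was about 0.

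**Bias in the planned repeated-measures model.** Earlier MED values recover part of this. Likelihood-based reruns with assumed between-visit correlations of 0.7-0.9 gave, at slopes of 0.4 and g = 10-16:

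- 1.7-3.0 MED if all loss precedes any follow-up, so nothing is recovered
- 1.0-2.0 MED if loss is spread over time
- 0.4-1.3 MED if loss is late
- 0.5-2.3 MED when 10-40% of those missing have no post-baseline data

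At slopes of 0.7 with g = 16, results ran from 1.0 to 3.7 MED.

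**The case against.** The strongest case on the other side has five parts.

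- **Baseline dose and institution are already in the primary model.** Arm-specific loss related to baseline dose is therefore conditioned on, whatever the screen shows. This stands, and it narrows the concern to other prognostic characteristics.
- **Completer-only bias is not the bias of the planned analysis.** A reader might take 2-3 MED, or 5 MED at the stronger slopes, as the expected error. The plan uses a repeated-measures model, which reduces the bias without removing it. The reduction is least for early loss, and the PROMIS outcomes have only month 6 as an earlier follow-up.
- **The scenario is special.** A reader might infer that the pooled model misses arm-differential attrition in general. It does not: one-arm and same-direction predictors are found as often or more often. But exact cancellation is not required either, as the +0.4/-0.2 row shows. No passage in the documents says how likely opposite signs are.
- **The text is open.** A reader might say that arm is excluded, that a pooled p-value is the switch, or that a null screen will be declared as no differential attrition. The predictor list is expressly non-exhaustive, no threshold is stated, and nothing says how a null screen will be read. Still, no interaction is planned, whereas SAP 9.6.4 writes one out in full where it is wanted.
- **The step is conditional and subsidiary.** SAP section 6 reports 20% study discontinuation, which is not the same as missing MED, so whether the trigger is met is unknown.

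**Conclusion.** The point holds in a limited form. As written, the screen is poorly matched to its own aim: it readily flags the near-harmless equal-slope pattern (about 95%) and flags the equal-and-opposite pattern at about its false-positive rate. An unflagged characteristic would not enter the adjusted sensitivity analysis.

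The size is modest. For a characteristic that predicts 12-month outcome beyond baseline dose, institution and earlier MED, residual bias is roughly 0.5-2 MED at slopes of 0.4, and up to about 2-4 MED at 0.7, against a 10-MED target. These figures rest on assumed slopes, loss rate, prognostic strength, correlation and timing of loss, none of which the documents give.

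The documents do not support reading this as an error in the primary analysis. The primary estimate and its test do not depend on the screen. This is a cheap improvement to a conditional sensitivity analysis.

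**What to change.** In SAP 9.4:

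1. Report the amount of loss and its baseline predictors separately by arm.
2. Keep the pooled main-effect screen, which is the better test for same-direction predictors. Alongside it, fit arm and arm-by-characteristic terms, or fit the model within each arm.
3. Carry a characteristic into the adjusted primary and secondary models if either its main effect or its arm interaction is associated with missingness. State the criterion in advance and interpret the screen descriptively.

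The cost is a few model terms and roughly twice as many screening comparisons, so an unneeded covariate may occasionally enter a sensitivity model. The primary analysis does not change.

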Objective	
To conduct a multisite pragmatic trial of two active interventions: shared decision making (SDM) as compared with cognitive behavioral therapy for chronic pain with motivational interviewing (MI+CBT-CP).
 
Primary Objective
 
 
• To assess if the interventions result in opioid dose reduction and compare their effectiveness.
 
 
Secondary Objectives
 
 
• To examine the impact of the interventions on physical function.
 
• To examine the impact of the interventions on pain interference.
 

---

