#### 5.3.1 Primary Analysis Methods for Opioid Usage Outcome

For reduction in opioid use, we will use a constrained linear mixed model to generate point and interval estimates of the reduction in opioid dose MED from baseline to **4, 6, 8, 10, 12, 14, 16, and 18** months and to test the hypothesis that this reduction differs between the 2 intervention arms. While the primary and secondary time assessments are at 6, 12 and 18 months, all available opioid prescription data from baseline through 18 months will be included in the model. This approach will provide consistent estimates and valid inferences under missing at random (MAR) data assumptions while accounting for correlation among multiple measures on the same participant. This mixed model will improve the power of the study and the precision of all estimates by allowing all available measures for an individual to be incorporated in the analysis, even if other timepoints are missing. The model will include fixed effects for the treatment group, time interval (as a categorical variable), treatment-by-time interaction, baseline opioid dose, the stratification effect of institution, and random effects for participant. An intervention-arm-specific Toeplitz correlation structure will be assumed for the within-participant measures, to reflect the changing correlation of these measures over time and permit the

correlation structure to differ between study arms. The model will be used to generate point and interval estimates and to test differences in mean changes in opioid dose between the 2 intervention groups at 12 months (primary timepoint) and to generate point and interval estimates at 6 and 18 months (secondary timepoints).

This model treats missing data as ignorably missing, assuming any missing data are missing at random, after accounting for baseline opioid dose. Sensitivity analyses based on multiple imputation procedures will be performed to evaluate departures from critical distributional and missing data assumptions. Plans to address missing data are further presented below (see *Missing Data Section*) and will be described in detail in the Statistical Analysis Plan. Assessments of model assumptions and goodness-of-fit will also be specified in the Statistical Analysis Plan.

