Although the MAR assumption is often reasonable, in this study it will be possible that even after controlling for other correlates of missingness and outcome data observed before participants are lost, likelihood of attrition may be associated with key outcomes of interest, including opioid use, physical function, and pain interference. Consequently, sensitivity analyses to the MAR assumption based on multiple imputation strategies to include control-based imputation as well as tipping-point analysis will be described in the Statistical Analysis Plan.

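### SAP 9.4 limits the only missing-not-at-random check of the primary outcome to a significant result with more than 20% missing MED, an unexplained narrowing of what the protocol planned

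*SAP*

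**What the plan says.** Protocol 5.3.1 says of the primary model: "Sensitivity analyses based on multiple imputation procedures will be performed to evaluate departures from critical distributional and missing data assumptions". The Missing Data part of Protocol 5.3.3 gives the reason. Even after adjustment, "likelihood of attrition may be associated with key outcomes of interest, including opioid use, physical function, and pain interference". It then says that multiple-imputation strategies to include "control-based imputation as well as tipping-point analysis will be described in the Statistical Analysis Plan". Neither place makes these analyses depend on a p-value or on a missing rate.

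SAP 9.4 plans one analysis under missing not at random. It "will only be conducted if the primary analysis identifies a statistically significant treatment group difference at 12 months in the ITT population". A second condition must hold at the same time, so that the analysis runs only "if the percentage of participants with missing MED at the 12-month timepoint is more than 20% in the ITT population". The method is to "impute missing outcomes in the intervention found to have a weaker change from baseline at varying percentages of the observed data", lowering MED, "until a statistically significant treatment group difference is no longer identified". Control-based imputation does not appear in the SAP.

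The other missing-data step in SAP 9.4 adds baseline covariates linked to missingness to the same mixed model. It too requires more than 20% missing, and it still assumes MAR.

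Three further passages bear on this:

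- SAP 9.2 scores days after the last prescription as zero only if a T2 or T3 survey says that opioids are no longer taken. With any other answer, or no survey, those days are missing.
- SAP 6 reports survey completion of about 60%.
- SAP 7.6 reads a nonsignificant result as inconclusive.

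**The concern.** The protocol wanted MAR examined because dropout may depend on opioid use, which is the primary outcome. That reason does not vanish when the p-value exceeds 0.05 or when 15% rather than 21% of values are missing. As written, a null result would be reported with an estimate and a confidence interval that rest on MAR alone, and no reader could tell whether missing data contributed. The tipping-point method cannot fill the gap, because it is defined only as a walk from significance to nonsignificance.

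MAR is open to doubt here for a specific reason. Under SAP 9.2, a participant who stops opioids, stays in care and returns no survey is missing although the true dose is zero. A participant who moved care and still takes opioids is correctly missing. SAP 9.6.3 concedes that the record cannot separate the two.

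**Working it through.** **Inputs.**
- SAP 6: difference 10 MED, adjusted SD 40, two-sided alpha 0.05, 80% power, 253 per arm, up to 12% missing prescription data, group size 8, ICC 0.01, 526 randomized, post hoc power 75%.
- Protocol 5.4: mean baseline dose 55 MED.
- The 20% missing rate is the SAP 9.4 threshold. The actual month-12 rate is not given.

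**The plan's own figures.**
- n per arm = 2 x (1.96 + 0.842)^2 x 40^2 / 10^2 = 252, against 253 stated.
- Power at 253 per arm is 80.3%.
- 506 x 1.2 = 607.2, stated as 608.
- At 526 randomized, 526/1.2 = 438 effective participants give 74.4% power, against 75% stated.

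These reproduce.

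**Precision at 526 randomized.** The design effect is 1 + (8 - 1) x 0.01 = 1.07. It is applied here to both arms, which is slightly conservative because only one arm is grouped. SE = 40 x sqrt(2 / n per arm), and power = Phi(10/SE - 1.96).

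| Missing | Effective total | SE | 95% CI half-width | Power for 10 MED |
|---|---|---|---|---|
| 12% | 526 x 0.88 / 1.07 = 432.6 | 3.85 | 7.5 | 73.9% |
| 20% | 526 x 0.80 / 1.07 = 393.3 | 4.03 | 7.9 | 69.8% |

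**How often the significance condition alone blocks the check.**
- No true difference: 1 - 0.05 = 95%.
- True difference of 10 MED: 25% at the SAP's stated 75% power, 26% from the 12% row and 30% from the 20% row.

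At 12% missing the second condition already fails, so the check does not run whatever the p-value.

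**Reach of non-ignorable missingness.** Suppose a share m of month-12 values is missing in one arm, and the true values differ by D from what MAR predicts. The arm difference then moves by m x D. Taking D as half the assumed baseline mean, 27.5 MED:
- m = 12%: 0.12 x 27.5 = 3.3 MED.
- m = 20%: 0.20 x 27.5 = 5.5 MED.

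The D that would pull an expected 10-MED difference down to the significance boundary, with one arm affected, is (10 - 7.54)/0.12 = 20.5 MED at 12% missing and (10 - 7.91)/0.20 = 10.5 MED at 20%. Equal shifts with equal missingness in both arms give zero.

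**Direction.** Unconfirmed stops scored as missing understate the reduction in the arm where they occur. If that arm has the larger true reduction, the difference shrinks. If it has the smaller one, the difference grows. Unequal survey confirmation by arm can act in either direction. The documents give neither stop rates nor survey response by arm.

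**The case against.** Several points on the other side have weight.

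- **The protocol leaves the details to the SAP.** It does, and a reader might infer a flat contradiction, which the text does not support. But Protocol 5.3.1 says that the analyses will be performed, and 5.3.3 names two methods. SAP 9.2, 9.3 and 9.6.3 each explain another departure from the protocol; 9.4 explains neither the conditions nor the dropped method. It is an unexplained narrowing.
- **A null result is only inconclusive under SAP 7.6.** So no claim of equivalence follows, and a wider grid would not change the formal conclusion. The estimate and interval will still be published and used, under MAR only.
- **A tipping point suits a significant result, and moving the weaker arm is the right challenge to one.** True. That justifies conditioning this tool on significance, but not having no other tool.
- **The protocol expects EHR dose data to be virtually complete, so a threshold is reasonable.** It is a rationale, but the SAP does not give it. At 12% missing, a one-arm shift of 27.5 MED still moves the difference by 3.3 MED.
- **Control-based imputation has no obvious reference in** "a multisite pragmatic trial of two active interventions". This stands, and one sentence in the SAP would settle it.

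A reader might also infer that the SAP 9.2 coding rule biases the trial toward no difference. The documents do not support that. The direction depends on which arm has more unconfirmed stops, and equal patterns cancel. The rule is a defensible primary choice. Nor does the 20% study discontinuation in SAP 6 show that the missingness condition will be met: it is not the missing-MED rate, and exactly 20% would not satisfy it.

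**Conclusion.** The concern holds as a gap in the sensitivity analyses. It does not show that the primary analysis is wrong. Under SAP 9.4 a null result never receives a missing-not-at-random check, and a significant one receives it only above 20% missing, which is more than the plan expects. The significance condition alone withholds the check in 95% of trials with no true difference and in about 25 to 30% with a true 10-MED difference (12 to 20% missing, 526 randomized, SD 40).

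What could go unseen is a shift of m x D, for example 3.3 to 5.5 MED, against an interval half-width of 7.5 to 7.9 MED. That illustration assumes non-ignorable missingness in one arm only, with D = 27.5. The true shift could be smaller, zero or of the opposite sign, and the documents cannot settle which. That uncertainty is the reason to run the check. This is a cheap improvement.

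**What to change.** 1. In SAP 9.4, delete the significance and 20% conditions. Run a delta-adjusted multiple-imputation analysis of month-12 MED whatever the primary result. Use a prespecified grid of shifts applied to each arm separately and to both, and report the estimate and 95% CI at every grid point. If the primary result is significant, report the tipping point as well.
2. Keep the primary outcome definition. Within the grid, include a bounding scenario that sets MED to 0 on unexplained days after prescription run-out. Limit it to days before each site's CDM data cut-off less the lag of up to 3 months (SAP 4.4.3 and 4.6), so that late-arriving records are not scored as stops. Label it a bound, because stopping and moving care cannot be separated (SAP 9.6.3).
3. Report by arm how many participants have post-run-out days coded 0 and how many have them coded missing.
4. State why control-based imputation was dropped, or name a reference arm and restore it.

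Fix these before arm-level results are seen, or label them post hoc.

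Cost: SAP wording and some programming on data already planned for extraction. Sample size, alpha, power and the primary definition do not change. The drawback is that the bounding scenario scores some patients who moved care as 0, so it must stay a sensitivity analysis.

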7.3 Handling of Dropouts and Missing Data

Analysis of the primary and secondary repeated measurement endpoints will be based on a repeated measures mixed model using data from all time points to account for missing data and thereby maximize information used for the analyses. The correlation of measurements between visits for a participant at earlier time points (including those who discontinue early) contribute to the model by reducing the standard error of the outcome over time, allowing us to have a tighter confidence interval at the primary timepoint (i.e., at 12-months). These models treat missing data as ignorable missing, assuming any missing data are missing at random (MAR); see Section 9.3 for more detail.

In the event of partially missing medication information for a prescription, we will calculate the daily MED and days supply based on other available prescription data and a series of assumptions vetted for reasonableness by prescribing study clinicians and by evaluation of consistency with other prescription data. All assumptions for calculating daily MED and days supply are described further in Section 9.2.

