9.5 Analysis of Secondary Outcomes

9.5.1 PROMIS Pain Interference and Physical Functioning

Secondary analyses will generate point and interval estimates of mean change in the PROMIS physical function and PROMIS pain interference T-scores from baseline to 6 and 12 months between the 2 intervention arms. The 12-month timepoint is primary. These secondary analyses will use appropriate linear mixed model-based approaches analogous to those described for the primary outcome analysis (section 9.3), to take advantage of the data from 6-month assessments for participants who did not complete the 12-month assessment as well as the correlation between the timepoints for participants with both assessments to estimate the change at 12-months for all participants with at least one post-baseline assessment.

Since comparisons at 12 months for these outcomes are two protocol-specified secondary analyses, statistical significance will be assessed with adjustment for multiple comparisons using the Hochberg modification to the Bonferroni adjustment. The Bonferroni adjustment is a simple function of the raw p-values and is computationally

quick but can be too conservative. Step-down methods remove some conservativeness, as do the step-up methods described by Hochberg (1988). The modification procedure rejects all hypotheses with smaller or equal p-values to that of any one found less than its critical value, defined as $(i/m)/Q$ (where I = the individual p-value rank; m = the number of tests; and Q = the false discovery rate). Essentially, if the largest p-value for these two comparisons is < 0.05 , then both tests are considered statistically significant. However, if the largest p-value is > 0.05 then the next largest p-value will be assessed for statistical significance (adjusting for multiple comparison) relative to the number of tests being performed (i.e.: $0.05/2 = 0.025$).

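### The two formally tested PROMIS outcomes have no missing-not-at-random sensitivity analysis, although about 40% of surveys are missing and the protocol names both as at risk of informative attrition

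*SAP*

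**What the plan says.** Protocol 5.3.3 (Missing Data) accepts that, even after conditioning on observed data, "likelihood of attrition may be associated with key outcomes of interest, including opioid use, physical function, and pain interference". It draws the consequence that "multiple imputation strategies to include control-based imputation as well as tipping-point analysis will be described in the Statistical Analysis Plan". It does not say which outcome gets which method.

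SAP 9.4 describes a single analysis of this kind: "We will explore one sensitivity analysis called a tipping point analysis". Its scope is explicit: "a sensitivity analysis will be conducted on the primary outcome to assess the robustness of the primary analysis results". It runs only if the primary result is significant and more than 20% of 12-month MED values are missing.

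For PROMIS, SAP 9.5.1 says: "These secondary analyses will use appropriate linear mixed model-based approaches analogous to those described for the primary outcome analysis". SAP 7.3 states the assumption behind the primary and secondary models: "These models treat missing data as ignorable missing, assuming any missing data are missing at random".

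One other analysis in SAP 9.4 does reach PROMIS. If a baseline characteristic predicts missing data, "a sensitivity analysis on both the primary and secondary outcome measures will be implemented", with that characteristic added as a covariate. The attrition model that feeds it has its own trigger: "This assessment will only be conducted if the percentage of participants with missing MED data at the 12-month timepoint is more than 20" percent.

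SAP section 6 reports survey completion of about 60% as of June 2023. Planned PROMIS missingness was 20% in that same section and 25% in protocol 5.3.3.

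**The concern.** The protocol's reason for going beyond MAR applies by name to both PROMIS outcomes, yet the SAP gives them no such analysis. The only check lies on the outcome drawn from the EHR, which the protocol expected to be virtually complete. The survey outcomes, with 1.6 to 2 times their planned missingness (40/25 and 40/20), have none.

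The covariate-adjusted model does not fill the gap. It is still a MAR analysis, its trigger is missing MED rather than missing surveys, and its attrition model describes EHR loss. That last feature comes from protocol 5.3.3; the 20% trigger is new in the SAP.

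At stake is a positive PROMIS claim. Protocol 5.1 has both outcomes formally tested whatever the primary shows. Only a departure from MAR that differs between arms would bias the comparison; one of equal size in both arms cancels.

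**Working it through.** **Inputs.** From SAP section 6: 526 randomized, about 60% survey completion, SD of change 10, minimally important differences (MIDs) of 3.5 (pain interference) and 2.0 (physical function), CBT group size 8 and intraclass correlation 0.01. Allocation is 1:1 (SAP 4.3). The observed difference d is an assumption.

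**1. Reproduce the plan's figures.** Power uses a normal approximation, two-sided 0.05.
- Planned: 608 × 0.75 / 2 = 228 per arm gives 96.2% and 57.0%, matching the stated 96% and 57%. The SAP's 20% missing (243.2 per arm) would give 97.1% and 59.7%, so the stated figures fit the protocol's 25%.
- Post hoc: 526 × 0.60 / 2 = 157.8 per arm. The design effect for group delivery is 1 + (8 − 1) × 0.01 = 1.07. With arm design effects a and b, SE = 10 × √((a + b) / 157.8).

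| Design effect | SE | Power, 3.5 | Power, 2.0 |
|---|---|---|---|
| Neither arm | 1.126 | 87.5% | 42.7% |
| CBT arm only | 1.145 | 86.3% | 41.5% |
| Both arms | 1.165 | 85.2% | 40.4% |

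SAP Table 6.1 gives 85% and 40%. The last row matches, but so would 292 to 296 completed surveys with no design effect, so the match does not settle which was used. All three rows are carried forward.

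**2. Departure that removes significance.** Let the arm difference among non-responders fall short of the responders' by δ. With missing share m, the overall estimate is (1 − m)d + m(d − δ) = d − mδ. Holding the SE fixed, significance is lost at δ = (d − z × SE) / m, where the non-responder effect is d − δ. Under Hochberg, pain interference is judged at 0.05 (z = 1.960) if physical function also reaches 0.05, and otherwise at 0.025 (z = 2.241).

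Example with no design effect, d = 3.5, m = 0.40: (3.5 − 1.960 × 1.126) / 0.40 = 3.23, leaving 0.27 among non-responders.

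| Missing | Assumed d | δ at 0.05 | δ at 0.025 |
|---|---|---|---|
| 40% | 3.0 | 1.8–2.0 | 1.0–1.2 |
| 40% | 3.5 | 3.0–3.2 | 2.2–2.4 |
| 40% | 4.0 | 4.3–4.5 | 3.5–3.7 |
| 30% | 3.5 | 4.6–4.9 | 3.6–3.9 |

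Ranges span the three design-effect cases. At 40% and d = 3.5 the non-responder effect is 0.3 to 0.5 (alpha 0.05) or 1.1 to 1.3 (alpha 0.025). At 30% (184.1 per arm, SE 1.042 to 1.078) it is −1.4 to −1.1 or −0.4 to −0.1, that is, reversed or close to zero.

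**3. Month-6 data.** As a favourable bound, assume month 6 is complete, its correlation with month 12 is 0.7, and there is no design effect: SE = √(2 × (100/263) × (0.49 + 0.51/0.60)) = 1.009. For d = 3.5 at 40% missing, δ becomes 3.8 and 3.1.

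**4. Check by simulation.** In 300 simulated trials with 20 imputations, δ = 3.23 in one arm and no month-6 data, the mean estimate was 2.26 with Rubin SE 1.14 (z = 1.98). This agrees with the formula.

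**5. Physical function.** At its MID of 2.0 the result is already non-significant, since 1.960 × 1.126 = 2.21 exceeds 2.0. No departure is computed for it.

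**The case against.** Protocol 5.3.3 does not assign methods to outcomes, and the only protocol text that ties multiple imputation to a specific model is 5.3.1, the MED model. So this is an omission measured against the protocol's reasoning, not a clear breach of a stated commitment. That stands, but the reasoning names both PROMIS domains.

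The illustration may also overstate fragility. SD 10 is the SD of change, whereas the planned model adjusts for baseline and may have a smaller residual SD. At 40% missing, d = 3.5 and no design effect, an assumed SD of 9 gives δ of 3.8 and 3.1, and an SD of 8 gives 4.3 and 3.7, which requires a reversed effect among non-responders (−0.8 and −0.2). The 60% figure is not tied to month 12, and month-6 data help. All this is fair. It widens the range of possible answers but does not provide an analysis. Conditioning on month 6 is still MAR and adds nothing for participants who missed both surveys.

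The 20% MED trigger could also open. SAP section 6 reports 20% discontinuation, and SAP 9.2 treats dose after the last prescription as missing unless a survey confirms that opioids were stopped. The documents do not show whether it will open. If it does, the PROMIS model it brings in remains MAR.

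Finally, with two active arms there is no natural reference for control-based imputation, so its absence may be sensible. It is unexplained, though, while SAP 9.3 and 9.6.3 do explain other departures from the protocol.

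The significance condition on the MED tipping point is not counted as a defect, because non-significant results are to be read as inconclusive.

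**Conclusion.** The concern holds. The SAP has no missing-not-at-random analysis for either PROMIS outcome, although both are formally tested, about 40% of surveys are missing, and the protocol expects that attrition may be informative for them. The primary analysis is not affected.

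The size is illustrative. Across the cases worked here for an assumed pain interference difference of 3.5, the arm-differential departure that would overturn significance runs from 2.2 to 4.9 points, against an MID of 3.5. The low end assumes 40% missing, SD 10, no use of month 6 and alpha 0.025; the high end assumes 30% missing and alpha 0.05. The figures show no actual bias. They show that the answer depends on facts the planned analyses would not examine.

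**What to change.** 1. In SAP 9.4 and 9.5.1, add a delta-adjusted (tipping-point) multiple-imputation analysis at month 12 for both PROMIS outcomes, run regardless of MED missingness and of the primary p-value. Vary delta separately by arm, in both directions, on a grid reaching at least 5 points (the largest departure above is 4.9). Report estimates and 95% CIs across the grid, and the point at which significance is lost.
2. Either restore control-based imputation and name the reference arm, or state in one sentence why it is omitted.
3. Base the PROMIS attrition model, and any missingness trigger kept for PROMIS, on survey non-response.
4. Optionally, drop the significance condition on the MED tipping point.

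The cost is SAP wording and a few SAS runs. No new data are needed, because survey completion is already tabulated for the CONSORT diagram (SAP 8.1). Reported robustness may look less favourable.
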